### 6. ADVERSE EVENTS

It is not anticipated that any adverse events will occur due to the nature of the study which consists of assessment, questionnaire and focus group which do not involve clinical invasive procedures. However, any questions concerning adverse events reporting will be directed to the Chief Investigator, and the sponsor

### 7. PATIENT AND PUBLIC INVOLVEMENT

The protocol has been reviewed by two patients and two caregivers (have experienced treatment for primary brain tumours). We will also include a patient and caregiver as part of the study management group to give their opinion on the design, management, discussion and dissemination of the study. These individuals will not be enrolled as participants in the study.

### 8. STATISTICS AND DATA ANALYSIS

The CI, [name], and Co-investigator, [name], will deal with the day to day management of the study and will ensure data completion and will help collate and check the data.

We will apply for the study to be NCRN-badged therefore if successful the local NCRN research nurses will be able to provide recruitment support. At Imperial College Health Care Trust, data will be collected in clinic on iPads, on Care Information Exchange (CIE – secure online platform currently available at ICHT) or on paper by the dedicated study team and stored directly onto ICHT Trust computers. At the other centres data will be collected in clinic using iPads/paper by the site-specific study team and stored on local secure NHS computers. At the end of each month data collected will be transferred to the main ICHT computer in a pseudonymised format for analysis.

#### 8.1 STUDY DESIGN AND SAMPLE SIZE

Our study design is based on a close reading of previous studies, and our target sample size is 130 patients and caregivers. Based on previous work, we estimated that a sample size of 80 patients is needed to allow for an analytical sample of 60 (Hogan *et al.*, 2013; Tang *et al.*, 2014; Aburub *et al.*, 2016b). We expect that not all caregivers will participate, and thus we allow for a differential recruitment of 50 caregivers. Previous work exploring the use of PGI has typically enrolled 30 - 80 patients. Our work should place us towards the top end of this range.

Formal statistical planning is difficult without knowing rates of completion and drop-out. However, if we want to estimate the concordance (as agreement between standard QoL measures and PGI) using Spearman's rank correlation coefficient, then there is a formula to calculate these confidence intervals. If we assume that the true correlation coefficient is ~0.5 (in line with previous work in 55 patients with traumatic brain injury and 192 patients with a range of cancers) then if we find an r =

0.5 and analytical n = 60 the 95% confidence intervals for the r value are 0.28 - 0.67. In the caregiver cohort, if calculated r = 0.5 and n = 30 then the 95% confidence intervals on r is 0.17 - 0.73.

We accept that these 95% confidence intervals are large (although in line with the literature) which is why this is a feasibility and pilot study.

The main aim of CaPaBLE is to demonstrate feasibility and acceptability of using the PGI and CaGI in patients with brain tumours and caregivers. We will assess face and content validity of the PGI by assessing areas of patients' lives affected by the cancer and the treatment and comparing those to domains in the standard measures.

#### 8.2 VALIDITY

We will assess face and content validity of the PGI by assessing areas of patients' lives affected by the cancer and the treatment and comparing those to domains in the standard measures. Overall the standard measures for patients capture 36 symptomatic and functional domains: 25 covered by the EORTC QLQ-C30 and a further 11 covered by the brain tumour module (BN20); for the caregivers the standard measure CarGoLQoL covers 10 domains. We will measure how many of these are covered by the PGI, and whether multiple PGI concerns lie within one domain, and whether PGI concerns lie outside the domains. We will represent this by reporting number and proportion of domains covered and number of a proportion of PGI concerns that were not captured in the standard measures. We will represent coverage with spider-web plots.

We will assess construct validity by assessing correlation between normalised standard measure scores and PGI scores. In line with previous work, we will also use Bland-Altman plots to assess this relationship.

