#### 3.4 QUESTIONNAIRES

Patients will be asked to complete the following questionnaires at certain study time points:

- PGI is a three-step process: Patients lists five areas most affected by illness and an initial box asks, "all other areas of your life affected by your cancer and treatment." Patient rates each of the 6 areas on a scale 0 (worst imaginable) to 6 (very best imaginable); Patient distributes 10 points between the 6 areas with the most points going to the more important areas
- EORTC QLQ30 covers five functioning scales (physical, social, role, cognitive, and emotional functioning), eight symptom scales (fatigue, nausea/vomiting, pain, dyspnea, sleep disturbances, appetite loss, constipation, and diarrhea), financial impact, and overall quality of life, and the scores are linearly converted to range between 0 to 100. High scores in the functioning scale and global QoL indicate better function whilst a higher score in the symptom scale indicate higher symptom burden.
- EORTC QLQ-BN20 questionnaire covers a further 11 scales to assess neurological deficits (visual disorder, motor dysfunction, communication deficit), future uncertainty, and disease- and treatment-related symptoms. Similar to the EORTC QLQ30 the raw scores are converted to a 0-100 scale and a higher score for this questionnaire represents a poorer QoL.
- EQ-5D-5L is a short, quick and cognitively undemanding assessment consisting of 5 questions and a Visual Analog Scale. It has been used in a wide range of health conditions and treatments and therefore makes it an ideal tool for comparative assessment. Furthermore, the EQ-5D-5L can then be adapted to a single index value.
- ACE 27 Questionnaire, taken at enrolment only by a member of the research study team. To assess background health status of patient.

Caregivers will be asked to complete the following questionnaires at certain study time points

- CaGI which will be based on the same concept as the PGI three-step process: Caregiver lists five areas most affected by illness and an initial box asks, "all other areas of your life affected by your loved one's cancer and treatment." Caregiver rates each of the 6 areas on a scale 0 (worst imaginable) to 6 (very best imaginable); Caregiver distributes 10 points between the 6 areas with the most points going to the more important areas

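### Section 8.2 counts 36 standard patient domains, but the scales listed in section 3.4 add up to 26 (24 or 25 on narrower counts), so patient coverage is understated if 36 is the denominator

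*Protocol*

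**What the plan says.** Protocol section 8.2 (Validity) sets out the content-validity analysis. For patients it says "Overall the standard measures for patients capture 36 symptomatic and functional domains: 25 covered by the EORTC QLQ-C30". The remaining 11 of the 36 are attributed to the BN20, and the caregiver instrument, the CarGOQoL, is given 10 domains. The section goes on to plan three things: the number and proportion of these domains covered by the PGI, the number and proportion of PGI concerns that the standard measures miss, and spider-web plots of coverage.

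Protocol section 3.4 (Questionnaires) describes the same patient instruments. Its entry for the first one reads "covers five functioning scales (physical, social, role, cognitive, and emotional functioning), eight symptom scales". The eight symptom scales are then named one by one, and the entry closes with two single scales, one for financial impact and one for overall quality of life. For the brain tumour module the section states "EORTC QLQ-BN20 questionnaire covers a further 11 scales".

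The two sections agree on the BN20 (11) but not on the QLQ-C30. The CarGOQoL count of 10 is the same in sections 1.1, 3.4 and 8.2.

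**The concern.** Section 8.2 fixes a number and then uses it. The sentence after the count says the study will measure how many of these are covered, so 36 is the natural denominator of the patient coverage proportion. If the instruments as described contain only 24 to 26 such units, ten or more of the 36 have no scale behind them. Coverage measured against 36 then cannot reach 100%, and the PGI looks less complete than it is. The bias runs in one direction, against the new measure, in the analysis that the protocol names for face and content validity (sections 8.1 and 8.2). A spider-web plot also needs a named axis for each domain, and the protocol supports no list of 36.

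**Working it through.** **Plan's own figure.** Section 8.2: 25 (QLQ-C30) + 11 (BN20) = 36. The addition is right, so the question is whether the 25 is.

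**Inputs from section 3.4.** QLQ-C30: functioning 5 (all named), symptom 8 (all named), financial impact 1, overall quality of life 1. BN20: 11.

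**Count and its variants.**

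| Units counted | QLQ-C30 | + BN20 | Total |
|---|---|---|---|
| All listed scales | 5 + 8 + 1 + 1 = 15 | 11 | 26 |
| Without overall quality of life | 5 + 8 + 1 = 14 | 11 | 25 |
| Also without financial impact | 5 + 8 = 13 | 11 | 24 |
| Section 8.2 as stated | 25 | 11 | 36 |

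The narrower counts are worth showing because 8.2 speaks of symptomatic and functional domains. Overall quality of life, and on a strict reading financial impact, may not qualify.

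**Can 25 be reached another way?** Adding the EQ-5D-5L to the 15 gives 15 + 5 = 20 (five questions) or 15 + 6 = 21 (with the visual analogue scale). Neither is 25. Counting individual questions does not explain the total either: section 1.1 gives 50 questions for the two questionnaires together, not 36.

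**Effect on the patient proportion if 36 is used.** Let k be the number of domains covered and D the number supported by section 3.4. The reported proportion is k/36 instead of k/D. The ratio of the two is D/36, whatever k is, and the highest reportable value (k = D) is also D/36.

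| D | Ceiling D/36 | Relative understatement 1 − D/36 |
|---|---|---|
| 26 | 72.2% | 27.8% |
| 25 | 69.4% | 30.6% |
| 24 | 66.7% | 33.3% |

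Examples with D = 26: 13 domains covered is 13/26 = 50.0% but would be reported as 13/36 = 36.1%; 20 covered is 20/26 = 76.9% but would be reported as 20/36 = 55.6%.

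**Quantities where 36 does not enter.** The number of patient domains covered is k itself. The proportion of PGI concerns not captured is divided by the number of concerns. Caregiver coverage is divided by 10.

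**The case against.** Section 8.2 says domains where 3.4 says scales. The word domain is not defined and the 36 are not listed, so a finer subdivision of the QLQ-C30 cannot be strictly excluded. Against this, the BN20 has 11 of each, so the protocol appears to use the two words for the same unit, and no finer subdivision is described anywhere. Equating the terms remains an inference, though the better supported one.

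The harm is also conditional. Assigning PGI concerns to domains and drawing the plot require a named list. Anyone who builds that list from section 3.4 would notice the discrepancy before dividing by 36. That stands: the stated number is wrong against the protocol's own description, but the bias arises only if that number is carried into the analysis.

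On importance, content validity is not among the outcomes named in section 3.8. Feasibility is assessed by completion rates, and section 8.1 calls this a feasibility and pilot study. No threshold, test or sample-size calculation depends on coverage, and the percentage can be recomputed from the number of domains covered. That also stands and limits the severity.

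Two stronger readings are tempting. A reader might infer that every coverage figure in the study will be wrong. The documents do not support that: the caregiver denominator is consistent, and two of the patient quantities do not use 36. A reader might also infer that the BN20 was counted twice, since 14 + 11 = 25. But 15 + 10 = 25 as well, which would fit the caregiver domains having been added by mistake. The protocol does not say how 25 arose, so either explanation is conjecture.

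**Conclusion.** The 25, and therefore the 36, in section 8.2 contradict section 3.4, which supports 15 and 26, or a total of 25 or 24 if overall quality of life, or that and financial impact, are left out. If 36 is used as written, the patient domain-coverage proportion is capped at 67–72% and understated by a relative 28–33%, and a patient plot on 36 axes is distorted in the same way. This rests on two assumptions: that a domain in 8.2 is a scale in 3.4, and that 36 is actually used as the denominator. The effect is confined to that proportion and plot. It should be fixed because a stated number is wrong and the correction is simple, but it does not affect the sample size, the completion-rate outcome or any decision rule.

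**What to change.** In section 8.2, replace the count of 36, with 25 from the QLQ-C30, by one that matches section 3.4: 26 = 15 + 11, or 25 = 14 + 11 with the exclusion of overall quality of life stated. If financial impact is also excluded, the count is 24 = 13 + 11, and that exclusion should be stated too. List the domains by name, and use that list both as the denominator of the patient coverage proportion and as the axes of the patient spider-web plot. Do this before coverage is analysed, so that the denominator is not chosen with the results in view. The caregiver count of 10 needs no change.

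The cost is one corrected sentence and a short list. No additional data, visits or participants are needed.

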#### 8.3 RESPONSIVENESS

We will assess responsiveness by examining correlations between normalised changes from baseline. However, this is subject to some statistical biases, and so we will attempt to model change, using baseline HRQoL values as a baseline variable. We will consider the use of repeated-measures ANOVA (RM-ANOVA). We will compare QLQ C30, PGI and EQ5D5L (patients) CarGoQoL, CaGI, EQ5D-5L as pairwise comparisons (3 comparisons for both patients and caregivers). We will also assess relationship between QLC C30 and CarGOQoL and CaGI and PGI (4 comparisons) and EQ5D-5L (1 comparison). We will account for within-patient clustering of scores in our analyses and examine the role of centre as a variable in determining HRQoL scores.

We will use stepwise backwards multiple regression to model the relationship between PGI and QLQ C30 and PGI and E5QD-5L and CaGI and CarGoQoL and CaGI and EQ5D-5L. We consider the use of splines for fitting non-linear responses.

We will examine patients who are under 40 and PS 0/1 vs. patients over 60 and PS 2+ and assess their QoL. We would expect the QoL in the latter group to be worse, and we will use this as a simple validation of conventional QoL measures and personalised novel measures.

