## Imperial College

## London

#### INTRODUCTION 1.

#### 1.1 BACKGROUND

Despite some advances in treatment, the prognosis for patients with high grade brain tumours remains poor, and it is well recognised that both the disease and its treatment have the potential to affect the day to day lives of patients and their caregivers. However, the only tools currently available to get a formal understanding of quality of life are long questionnaires which do not allow for individuals to express their own opinions about what is important to their lifestyle. Moreover, "quality of life" is a difficult concept to define as its meaning may be different to different people. In addition, the nature of a patient's symptoms due to brain tumours, notably their degree of cognitive impairment, can be a barrier for questionnaire completion. For these reasons, the completion of HRQoL questionnaires, even within the context of a clinical trial, remains poor ((Taphoorn et al., 2010; Wick et al., 2016; Bitterlich and Vordermark, 2017).

Of note when discussing Quality of Life assessment is need to clarify the various terms used within the accompanying literature. Resulting from the diversity of intended uses, there are a variety of terms and associated assessment tools. Terms like "health status" are associated with a persons' disease state and physical performance, these are often clinician reported outcomes and include scales such as the ECOG Performance Scale and Adult Comorbidity Evaluation 27. "Quality of life" is seen as the most subjective term which is associated with an individuals' overall well-being and their view in comparison to expectations (own and societal); QoL questionnaires will include items on standard of living, social integration and personal relationships. "Health Related Quality of Life" is understood to be the impact on QoL in response to health state, this term can incorporate many domains and related questionnaires would include items covering self-care, pain and depression these patient reported outcome tools most commonly used during clinical trials.

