# Imperial College Healthcare

#### 3.1 SAMPLE SIZE

The target sample size for this observation, longitudinal study is 130 (80 patients and 50 caregivers), using a 20% patient and caregiver dropout rate. Our study design is based on a close reading of previous studies. Based on previous work, we estimated that a sample size of 80 patients is needed to allow for an analytical sample of 60. We expect that not all caregivers will participate, and thus we allow for a differential recruitment.

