#### 5. ASSESSMENT AND FOLLOW-UP

Patients will undergo standard follow up procedures (both clinical and imaging assessment) as part of their routine clinical care (monthly if on chemo-radiotherapy and 3-6 monthly during the follow up), and for this study will be followed from enrolment until 6 months. We intend to complete both patient and caregiver assessments at the same clinic visits. At all visits, the PGI/CaGI will be completed prior to any other assessment (EORTC QLQ30, BN20, CarGOQoL and EQ-5D-5L). At each visit the PGI/CaGI is completed anew, this will allow assessment of change in domains highlighted and the weighting ascribed to them.

To assess their previous medical history and concurrent medical conditions, the attending medical professional or researcher will complete the Adult Co-Morbidity Evaluation 27 with the caregiver at enrolment.

Patients and caregivers will be free to withdraw from the study at any time.

For validation purposes, on three visits patients and caregivers will be required to complete an additional assessment, EQ-5D-5L. This is a short, quick and cognitively undemanding assessment consisting of 5 questions and a Visual Analogue Scale. It has been used in a wide range of health conditions and treatments and therefore makes it an ideal tool for comparative assessment. Furthermore, the EQ-5D-5L can then be adapted to a single index value.

The end of the study is at the end of 6 months of follow up, discontinuation of treatment or death

		Enrolment/ Baseline	Week 2	Week 6	Month 3	Month 4	Month 6	Unexpected Visit
Patient	Demographic information	+						
	Medical history	+						
	Adult Co-Morbidity Evaluation 27	+						
	Diagnosis	+						
	MOCA assessment	+			+		+	
	EQ-5D-5L	+			+		+	
	Clinical information, Medication and imaging results	+	+	+	+	+	+	+
	ECOG PS	+	+	+	+	+	+	+
	Recent hospitalization	+	+	+	+	+	+	+
	PGI	+	+	+	+	+	+	+
	EORTC QLQ C30 & BN20	+	+	+	+	+	+	+
		Enrolment/ Baseline	Week 2	Week 6	Month 3	Month 4	Month 6	Unexpected Visit
Caregiver	Demographic information	+						
	Adult Co-Morbidity Evaluation 27	+						
	EQ-5D-5L	+			+		+	
	ECOG PS	+	+	+	+	+	+	+
	CaGI	+	+	+	+	+	+	+
	CarGOQoL	+	+	+	+	+	+	+

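### The only longitudinal model that section 8.3 names, repeated-measures ANOVA, is poorly suited to the missed visits and dropout the protocol expects; a mixed model using all available visits should replace it

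*Protocol*

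**What the plan says.** Protocol section 8.3 starts from correlations between normalised changes from baseline and concedes that these are subject to bias. It continues: "we will attempt to model change, using baseline HRQoL values as a baseline variable". The next sentence names the candidate model: "We will consider the use of repeated-measures ANOVA (RM-ANOVA". Later in the section comes "We will account for within-patient clustering of scores in our analyses", with a commitment to examine centre. The other named regression, "We will use stepwise backwards multiple regression to model the relationship between PGI and QLQ C30", is not a longitudinal model as written. No linear mixed model or estimating-equation method is named.

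Other sections describe the data this model would meet:

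- Section 1.1: "the completion of HRQoL questionnaires, even within the context of a clinical trial, remains poor", with cognitive impairment given as one barrier.
- Section 3.1: the sample size is set "using a 20% patient and caregiver dropout rate".
- Section 3.5, item 11, and section 5: follow-up can end early at death or when treatment is discontinued.
- Sections 3.6 and 4.3: a patient who loses capacity is withdrawn and no further data are collected.
- Section 5 schedule: PGI or CaGI and the main standard questionnaires at six planned time points. Section 3.5, item 10, lists five and omits week 2.

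**The concern.** Classical repeated-measures ANOVA works on a complete participant-by-visit table. A participant with one missed form is dropped entirely, and the scores that were collected go unused. That is tolerable when nearly everyone completes nearly everything, but this protocol says the opposite about its own population. Some of the expected causes of missing data (death, loss of capacity) are tied to health, so data missing completely at random, the condition under which complete cases are safely unbiased, is hard to assume.

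At stake are the responsiveness analysis, the part of primary outcome 3 that concerns variation and stability over time (section 3.8), and objectives 3 and 4 on tracking change through treatment and progression (section 2.2).

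**Working it through.** **1. The protocol's own precision figures.** Section 8.1 gives 95% intervals for r = 0.5. By Fisher's z, tanh(atanh(0.5) ± 1.96/√(n − 3)):

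- n = 60: tanh(0.549 ± 0.260) = 0.28 to 0.67.
- n = 30: tanh(0.549 ± 0.377) = 0.17 to 0.73.

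Both reproduce. They are intervals for a correlation and do not require every visit to be complete.

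**2. Participants that classical repeated-measures ANOVA would keep.** Section 8.1 states "a sample size of 80 patients is needed to allow for an analytical sample of 60" and uses 30 caregivers for its caregiver interval. No per-visit completion rate is given, so q is an assumption, taken as independent across visits with baseline always present. With k planned visits, complete cases = N × q^(k − 1).

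| q (assumed) | 60 patients, k = 6: 60q⁵ | 60 patients, k = 5: 60q⁴ | 30 caregivers, k = 6: 30q⁵ | 30 caregivers, k = 5: 30q⁴ |
|---|---|---|---|---|
| 0.95 | 46.4 | 48.9 | 23.2 | 24.4 |
| 0.90 | 35.4 | 39.4 | 17.7 | 19.7 |
| 0.80 | 19.7 | 24.6 | 9.8 | 12.3 |

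Starting instead from 80 patients less 20% dropout, 80 × 0.80 = 64, six visits leave 49.5, 37.8 or 21.0.

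**3. Precision and bias.** A simulation compared complete cases with a likelihood model using all available scores. All its settings are assumed: 80 patients, six visits, SD 20, true change −12, about 20% dropout by month 6 and 10% of forms missed at random. It used 120 to 150 replicates per scenario. About 37 to 39 of 80 patients were complete.

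| Dropout depends on | Complete-case change (SE) | All-data likelihood change (SE) |
|---|---|---|
| Nothing (completely random) | −12.0 (2.8) | −12.1 (2.3) |
| Last score, equal correlations | −12.3 (2.6) | −11.8 (2.4) |
| Last score, correlation fading with time | −12.6 (4.0) | −11.7 (3.0) |
| Decline from baseline, equal correlations | −10.1 (3.1) | −11.9 (2.4) |
| Decline from baseline, correlation fading with time | −9.5 (3.7) | −11.9 (2.8) |

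The complete-case standard error is larger in every row. The bias is nil in the first row. In the next two rows it is small (0.3 to 0.6 points) and towards too much decline. In the last two it is about 2 to 2.5 points towards too little. The Monte Carlo error of a complete-case mean is about 0.2 (2.8/√150) to 0.4 (4.0/√120), so the small departures are barely distinguishable from none and the larger ones are clear.

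**The case against.** The strongest reply is that nothing has been fixed. Section 8.3 says only that the method will be considered, and the final model and missing-data rules may sit in a statistical analysis plan that is not shown. The same section already promises baseline adjustment, allowance for within-patient clustering and a look at centre, which are most of the ingredients of a mixed model. This stands as a limit on severity. It does not remove the point, because repeated-measures ANOVA also models within-person correlation. The clustering promise therefore does not exclude it and does not protect a participant with a missed form.

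The arithmetic is also open to challenge. Applying a completion rate to 60, a figure already reduced from 80, may count some attrition twice. Death and loss of capacity produce dropout rather than independent gaps, and with 20% dropout and no other missed forms 64 of 80 patients would be complete. Section 3.5 offers continued, possibly remote, assessment after treatment stops, so that cause is less certain than death or loss of capacity. All of this is fair: the counts illustrate a range and are not forecasts.

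Three stronger readings are tempting but unsupported:

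- *Change would be understated.* That holds in the simulation only when dropout follows decline from baseline. Under other mechanisms the bias is nil or slightly the other way.
- *The 60 and 30 analytical samples would not be delivered.* Those figures support Spearman intervals, which the choice of model for change does not affect.
- *Including EQ-5D-5L would throw away the other visits.* Section 5 says "on three visits patients and caregivers will be required to complete an additional assessment, EQ-5D-5L". No method can pair it with PGI at visits where it is not collected. Analyses confined to those three visits lose less: 60q² gives 54, 49 or 38 patients.

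**Conclusion.** The point holds as a mismatch between the one longitudinal model named and the missing data the protocol itself predicts. If used in its classical form, that model would keep roughly three quarters of otherwise followed patients at 95% per-visit completion, about 60% at 90% and a third at 80% on the six-visit schedule, and somewhat more on the five-visit list. These proportions rest on assumed, independent completion.

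The loss of precision does not depend on why data are missing. Bias in change is a plausible risk, given withdrawal on loss of capacity, but neither its size nor its direction can be read from the protocol. A reader might infer that section 8.3 commits the study to deleting incomplete participants; its wording does not go that far. The change is worth making now because it is nearly free.

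**What to change.** Replace the repeated-measures ANOVA sentence in section 8.3 with wording such as:

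> Change will be analysed with a likelihood-based linear mixed model for repeated measures using all available visits, with visit, baseline score and centre as fixed effects and a participant random effect or an unstructured covariance.

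Every participant with a baseline and at least one later score then contributes, and the baseline, clustering and centre commitments already in section 8.3 are met by one model. An unstructured covariance over five post-baseline visits has 5 × 6/2 = 15 parameters, so the participant random effect is the natural fallback in the smaller caregiver cohort.

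Add two things:

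- One simple sensitivity analysis for health-related dropout, for example a delta adjustment that shifts the unobserved scores by a range of stated amounts. A pattern-mixture model by last visit would be too thin: 20% of 80 is 16 patients over five patterns, about 3 each, and 20% of 50 is 10 caregivers, 2 each.
- A statement of how scores after death and after loss of capacity are treated. A mixed model does not settle this by itself, since it implicitly projects scores beyond death.

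Sections 3.5 and 5 should also be reconciled on whether week 2 is an assessment, because that sets the number of repeated measures.

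The cost is protocol or analysis-plan wording and a little more analysis. Visit, baseline score and centre are already available, so no new data are needed. The downside is that the main model relies on missing at random, which the sensitivity analysis is there to probe.

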### 4. PARTICIPANT ENTRY

#### 4.1 INCLUSION CRITERIA

#### Inclusion Criteria -Patient

- 1. Newly diagnosed, or recurrent, high-grade primary brain tumour. We define a high-grade tumour as any grade 3 or 4 primary brain tumour (including meningioma).
- Newly diagnosed patients intending to undergo neurosurgical biopsy or resection, or to start a course of radical (≥45Gy) radiotherapy or a course of chemoradiotherapy or stereotactic radiotherapy.
- **3.** Recurrent brain tumours patients undergoing further treatment including surgery, chemotherapy or re-irradiation.
- 4. Performance status 0, 1, or 2
- 5. Able to provide written informed consent.
- 6. Intention to attend at least 5 clinic visits over a six-month period to the study site
- 7. Age 18 years and above
- 8. Willing to undertake study-specific measures

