#### 4.2 EXCLUSION CRITERIA

Exclusion Criteria -Patient

- 1. Diagnosed with a low-grade brain tumour (including grade 1 and 2 meningiomas)
- 2. Poor performance status (PS 3,4) or rapidly deteriorating fitness and for best supportive care and/or symptom control only.
- 3. Diagnosed with a high-grade brain tumour but not planned for any intervention.
- 4. Language barriers
- Poor cognition status based on clinical assessment/ Montreal Cognitive Assessment (MoCA)/ MDT
- 6. Refusal to participate

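### Section 8.3 validates the QoL measures by comparing two extreme age-and-PS groups, which leaves most patients out and makes the check imprecise; an all-patient regression would use data already collected.

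*Protocol*

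**What the plan says.** Section 8.3 of the protocol sets out a known-groups check: "We will examine patients who are under 40 and PS 0/1 vs. patients over 60 and PS 2+ and assess their QoL". It expects worse QoL in the older, less fit group and states the purpose: "we will use this as a simple validation of conventional QoL measures and personalised novel measures". It gives no group sizes and no expected difference.

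The population is wider than the two groups. Section 4.1 admits "Age 18 years and above" and "Performance status 0, 1, or 2"; section 4.2 excludes "Poor performance status (PS 3,4) or rapidly deteriorating fitness". For numbers, section 8.1 says "we estimated that a sample size of 80 patients is needed to allow for an analytical sample of 60". The schedule in section 5 collects demographics, ECOG PS, PGI, QLQ-C30 and EQ-5D-5L from every patient at baseline, and repeats ECOG PS at every later visit.

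**The concern.** Eligible patients who fit neither definition contribute nothing to this check: everyone aged 40 to 60, everyone under 40 with PS 2, and everyone over 60 with PS 0/1. From about 60 patients, two small groups may remain.

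The result is meant to speak to the validity of the standard tools and of the new index. With few patients per group, a real difference may be estimated so loosely that the check neither supports nor contradicts either kind of measure. The omitted patients would have been informative, and their data are already in hand. The choice of groups is fixed in the protocol, so this is not a detail left for a statistical analysis plan.

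**Working it through.** **The plan's own figure.** The only stated precision is for a correlation: "0.5 and analytical n = 60 the 95% confidence intervals for the r value are 0.28 - 0.67". The Fisher interval is tanh(atanh(0.5) ± 1.96/√(60 − 3)) = 0.282 to 0.669, which agrees. It uses all 60 patients and says nothing about the known-groups check.

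**Inputs.** N = 60 is from section 8.1. The age and PS mix is not in the protocol. I assume 10-25% under 40, 35-50% over 60 and 20-30% PS 2, with age and PS independent. A further case lets PS worsen with age: 25% under 40 (10% of them PS 2) and 50% over 60 (50% of them PS 2).

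**Group sizes.**
- Young and fit = 60 × P(under 40) × P(PS 0/1 among them)
- Older with PS 2 = 60 × P(over 60) × P(PS 2 among them)

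**Precision.** The 95% half-width in SD units, with n₁ and n₂ rounded, is t(0.975; n₁+n₂−2) × √(1/n₁ + 1/n₂).

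| Under 40 / over 60 / PS 2 | Groups | Total of 60 | Half-width |
|---|---|---|---|
| 10% / 35% / 20% | 4.8 and 4.2 | 9.0 | 5 v 4: 2.365 × 0.671 = 1.59 |
| 10% / 50% / 30% | 4.2 and 9.0 | 13.2 | 4 v 9: 2.201 × 0.601 = 1.32 |
| 25% / 35% / 20% | 12.0 and 4.2 | 16.2 | 12 v 4: 2.145 × 0.577 = 1.24 |
| 25% / 50% / 30% | 10.5 and 9.0 | 19.5 | 11 v 9: 2.101 × 0.449 = 0.94 |
| PS worsens with age | 13.5 and 15.0 | 28.5 | 14 v 15: 2.052 × 0.372 = 0.76 |

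If all 80 enrolled patients count at baseline, the independent mixes give 12 to 26 of 80, at most 14 v 12 in the largest case.

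**Power of the two-group comparison.** Two-sided 5% t-test, noncentrality d√(n₁n₂/(n₁+n₂)):

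| Groups | d = 0.8 SD | d = 1.2 SD |
|---|---|---|
| 4 v 6 | 19% | 37% |
| 9 v 9 | 36% | 67% |
| 12 v 12 | 47% | 80% |
| 14 v 15 | 55% | 88% |

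**Same contrast from all patients.** The like-for-like comparison keeps the young-fit versus old-PS 2 contrast and estimates it by regression on PS and age. Take the midpoints of the independent ranges: 17.5% under 40, 42.5% over 60, 25% PS 2, with age roughly Normal and linear in effect.
- Two groups: 60 × 0.175 × 0.75 = 7.9 and 60 × 0.425 × 0.25 = 6.4. For 8 v 6 the half-width is 2.179 × √(1/8 + 1/6) = 1.18 SD.
- Distance between the mean ages of the two tails, in SDs of age: φ(0.935)/0.175 + φ(0.189)/0.425 = 1.47 + 0.92 = 2.39.
- Regression: variance = 2.39²/60 + 1/(60 × 0.25 × 0.75) = 0.095 + 0.089 = 0.184. The half-width is 2.002 × √0.184 = 0.86 SD.

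So the same contrast has a half-width of about 0.86 rather than 1.18 SD. This comparison needs no assumed effect size, but it does depend on the assumed mix and on a linear age effect.

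**The case against.** The strongest objection is that extreme groups are chosen because they should differ more. Giving the two-group comparison and a PS-only comparison the same 0.8 SD would favour the latter. If the extreme groups differ by 1.2 SD, 9 v 9 has 67% power. If PS alone gives 0.5 SD, 48 v 12 has only 33%, and the ranking reverses. This stands, and it rules out quoting a set power gain for a PS-only split. It does not rescue the restriction, because an all-patient regression can estimate the same extreme contrast while using everyone.

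Other points also stand:
- **Small groups are inferred.** No age or PS mix is stated. Using more than half the sample would need an unusual mix, such as 60% over 60 with 70% of them PS 2, plus 15% under 40.
- **No formal test is named.** The power figures only illustrate; the interval widths carry the argument.
- **The check is auxiliary.** Section 8.2 assesses construct validity by correlation and Bland-Altman plots without restricting age or PS. Section 8.1 makes feasibility the main aim and accepts wide intervals for a pilot.

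A reader might infer that PS 2+ is an error because PS 3 and 4 are excluded. The documents do not support that. ECOG PS is repeated at every visit, so higher values can arise later, and at baseline the label selects the same patients as PS 2. A reader might also hold that combining age with PS invalidates the check. A known-groups check needs groups expected to differ; it need not assign the difference to one cause.

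**Conclusion.** The point holds in a limited form. The exclusion of patients between and across the two definitions follows directly from section 8.3. Its size rests on assumed mixes: about 9 to 20 of 60 patients used if age and PS are independent, and about 29 if PS worsens with age. The corresponding half-widths are about 0.9 to 1.6 SD, and 0.76 SD in the most favourable case. At the weaker end the check would be uninformative even for a difference of 1.2 SD; at the favourable end it would detect a difference that large fairly well.

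It would go too far to say that the check will fail, that a null result will be taken as failure of the PGI, or that the remedy brings a fixed gain in power. The gain depends on age and PS effects that the protocol does not give. The patients are missing from this check only, not from the other analyses. The change is worth making because it is a better use of data already collected, not because the study's main aim is at risk.

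**What to change.** In section 8.3, make the known-groups check a baseline regression in all patients with data. Fit PGI, QLQ-C30 and EQ-5D-5L in turn on PS (0-1 versus 2, or ordinal) and continuous age. For each measure report, with 95% intervals, the PS effect and the combined contrast between a young patient with PS 0/1 and an older patient with PS 2, on a standardised scale so that the measures can be compared. Name the two ages used in that contrast. Keep the present two-group comparison as a descriptive summary with its group sizes.

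The cost is wording and a little more analysis; no new data are needed. The one statistical price is an assumed form for the age effect. Section 8.3 already contemplates splines for non-linear responses, so that form can be checked. The PS 2+ label need not change.
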